8.2. Analyses of Key Secondary Serum Immunogenicity (IgG) Endpoints

Descriptive statistics (GMT, GMFR) for serum IgG against PT, FHA, and PRN will be presented at baseline and Day 29 and by treatment group (BPZE1 + Boostrix, Boostrix).

The non-interference objective will be tested as non-inferiority of BPZE1+Boostrix group compared to the Boostrix group.

The formal non-inferiority hypothesis is:

$$H_0: \frac{\mu_{BBP}}{\mu_B} \leq 0.5 \text{ vs. } H_A: \frac{\mu_{BBP}}{\mu_B} > 0.5$$

Taking the natural log transformation,

$$H_0: \ln(\mu_{BBP}) - \ln(\mu_B) \leq -0.693 \text{ vs. } H_A: \ln(\mu_{BBP}) - \ln(\mu_B) > -0.693$$

Where μ_{BBP} is the GMT for the BPZE1+Boostrix group and μ_B is the GMT for the Boostrix group.

For serum IgG against PT, FHA, and PRN at Day 29, separate ANCOVA models that include baseline IgG levels and treatment group as covariates will be used to compare the natural log-transformed GMTs between BPZE1 + Boostrix and Boostrix groups. The 95% CI for between group difference in GMT will be calculated in two steps: 1) calculate the 95% CI on natural log scale; 2) exponentiate the lower and upper limits to get the 95% CI on the original scale.

Non-inferiority, or non-interference, will be demonstrated if the lower limit of the 95% CI of between group difference in natural log-transformed GMTs is greater than -0.693.

For serum IgG against diphtheria and tetanus, the non-interference objective will be tested as non-inferiority of BPZE1+Boostrix group compared to the Boostrix group for the proportion of subjects with antibody concentration ≥ 0.1 IU/mL.

The formal hypotheses is:

$$H_0: \pi_{BBP} - \pi_B \leq -0.1 \text{ vs. } H_A: \pi_{BBP} - \pi_B > -0.1,$$

where π_{BPP} is the proportion of subjects with antibody (diphtheria or tetanus) concentration ≥ 0.1 IU/mL for the BPZE1+Boostrix group and π_B is the corresponding proportion for the Boostrix group.

The 95% CI for between group difference in the proportion of subjects with antibody concentration ≥ 0.1 IU/mL will be calculated using the Agresti-Caffo method. Non-inferiority, or non-interference, will be demonstrated if the lower limit of this 95% CI is greater than -0.1.

Sensitivity analysis for key secondary endpoints will be performed based on the Immunogenicity Analysis Set.

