BPZE1 in a liquid formulation has been studied at various doses from 10^3 to 10^9 colony-forming units (CFU) in two Phase 1 clinical studies in Sweden with no vaccine-related serious adverse events (SAEs) and comparable general adverse events (AEs) to placebo controls. Most recently, in a Phase 2b study conducted in the US, BPZE1 (or BoostrixTM) was given as a single vaccination supplied in a lyophilized vial for reconstitution prior to intranasal administration via the intranasal mucosal atomization device (MAD) and then a re-vaccination/attenuated challenge was given 3 months later with BPZE1 (or placebo) to 300 healthy adults aged 18 to 50 years. BPZE1 (but not Boostrix) was shown to induce mucosal secretory immunoglobulin A (S-IgA) as measured by whole cell extract (WCE), filamentous hemagglutinin (FHA), and pertactin (PRN) assays, and these antibodies were sustained through 9 months (end of study [EOS]). Unlike Boostrix, the BPZE1-induced mucosal immunity was associated with protection from *B. pertussis* acquisition (colonization) using an attenuated challenge with BPZE1 3 months later. In addition, BPZE1 induced systemic immunoglobulin A (IgA) and immunoglobulin G (IgG) anti-pertussis antibodies (WCE, PT, FHA and PRN), which were sustained above baseline through the 9 months of study. A single vaccination appeared sufficient to induce both mucosal and systemic responses in this population. In addition, systemic and nasal/respiratory reactogenicity was overall none to mild, similar to Boostrix/placebo in intensity, with average

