4.1.2 Exclusion Criteria

Subjects meeting any of the following criteria (by review of medical history and subject intake) will be excluded from the study:

1. The subject has a history of pertussis-containing vaccination (inclusive of school vaccination programs) or documented *B. pertussis* infection within 3 years prior to Day 1 and/or a history of Td-containing vaccination (without pertussis vaccine component) within 1 month prior to Day 1.

2. The subject has a chronic significant illness actively being treated or a history of recent intervention for worsening or fluctuating symptoms (at the discretion of the investigator).
3. The subject has a history of cancer (malignancy).
4. The subject has a congenital, hereditary, or acquired disease or disorder classified as autoimmune, immunodeficient, coagulopathy, hepatic, renal, neurologic (including a history of Bell's palsy), or moderate to severe cognitive. (Attention deficit hyperactivity disorder permitted.)
5. The subject currently uses smoking products (including vaping and e-cigarettes) and is unwilling to refrain from use from Day 1 through Day 29 following any study vaccination.
6. The subject has received immunoglobulin, blood-derived products, systemic corticosteroids (at a dose of >10 mg per day for more than 10 days), or other immunosuppressant drugs within 90 days prior to Day 1.
7. The subject has any chronic pulmonary disease requiring active medication or pulmonary therapies, with the following exceptions:
 - a) Subjects with exercise-induced bronchospasm, if currently well controlled, who are willing to refrain from intense exercise for 7 days following study vaccination or
 - b) Subjects with Step 1 (intermittent) asthma classification who have not had an exacerbation requiring oral systemic corticosteroids in the past year; have an FEV1 documented to be >80%; do not have restrictions in normal activity due to breathing issues; and have used a short-acting beta-agonist less than or equal to 2 days per week over the past 2 months.

NOTE: Subjects in the safety lead-in cohort are not allowed to have these exceptions.

8. The subject has a history of oro/nasopharynx surgery (eg, adenoidectomy, tonsillectomy) within 60 days prior to Day 1.
9. The subject has a known hypersensitivity to latex or any component of any study vaccine. Specific to Boostrix: the subject has known hypersensitivity to neomycin or

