7.2 Blinded Sample Size Recalculation

A blinded sample size recalculation may occur when immunogenicity data for approximately 40 to 60 subjects per group are available. The standard deviation of the Day 29 change from baseline of S-IgA for WCE of natural logarithmic transformed GMFR will be computed. The standard deviation of natural logarithmic transformed GMTs of the IgG serum responses for the Boostrix-containing antigens (PT, FHA, PRN) at Day 29 will also be computed.

Proportions with titer ≥ 0.1 IU/mL for the IgG serum responses for the Boostrix-containing antigens (diphtheria, tetanus) at Day 29 will be estimated.

The standard deviations and proportions with titer ≥ 0.1 IU/mL will be computed in the full dataset and not by treatment group to ensure that the blinding is maintained. The sample size will then be recalculated with the potential to adjust the sample size accordingly.

A small committee consisting of select ILiAD leadership and an independent blinded statistician will evaluate the need to change sample size. The independent blinded statistician will use the standard deviation values estimated from the full dataset to recalculate the sample size. In addition to these pooled standard deviation values, the committee will also assess data completeness for the primary endpoint and drop-out rate.

The committee will meet and document its decision in a memorandum. This memorandum will include the pooled standard deviations, the updated power/sample size computations, and the final decision regarding any change in sample size.

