4.1.2. Sample Size for Key Secondary Endpoints

To demonstrate non-interference of IgG serum responses for the Boostrix-containing antigens (diphtheria, tetanus) at Day 29 when BPZE1 is co-administered with Boostrix (BPZE1 + Boostrix vs Boostrix), the test for non-inferiority of BPZE1 + Boostrix to Boostrix for the proportion with titer ≥ 0.1 IU/mL (for diphtheria, tetanus) has power exceeding 92% with approximately N=120 subjects per treatment group, assuming a noninferiority margin of 0.1, one-sided significance level of 0.025, 10% drop-out rate and the proportion with titer ≥ 0.1 IU/mL for the Boostrix treatment being at least 0.95.

Table 4-1 Power for Non-Inferiority of BPZE1/Boostrix to Boostrix for the proportion of titer ≥ 0.1 IU/mL

Parameter			Power ^{**}			
p_B [*]	$p_{BBP,0}$ ⁺	$p_{BBP,1}$ [#]	N=120***	N=135***	N=150***	N=165***
0.92	0.82	0.92	77.3%	81.8%	85.7%	88.7%
0.95	0.85	0.95	92.1%	94.6%	96.5%	97.7%
0.97	0.87	0.97	99.1%	99.0%	99.8%	99.9%

^{*}: p_B is the proportion of titer ≥ 0.1 IU/mL for the Boostrix treatment

⁺: $p_{BBP,0}$ is the proportion of titer ≥ 0.1 IU/mL for the BPZE1/Boostrix treatment under the null hypothesis H_0

[#]: $p_{BBP,1}$ is the proportion of titer ≥ 0.1 IU/mL for the BPZE1/Boostrix treatment under the alternative hypothesis H_1

^{**}: with one-sided significance levels of 0.025 and non-inferiority margin of 0.1

***: Effective sample size accounts for 10% dropout. For sample size of 120, 135, 150, 165 per group, the effective sample size is 108, 121, 135, 148, respectively, after accounting for 10% dropout.

To demonstrate non-interference of IgG serum responses for the Boostrix-containing antigens (PT, FHA, PRN) at Day 29 when BPZE1 is co-administered with Boostrix (BPZE1 + Boostrix vs Boostrix), the tests for non-inferiority of BPZE1 + Boostrix to Boostrix for each of the three IgG parameters (PT/FHA/PRN) have power of 97%, 100%, and 88%, respectively, for detecting between group differences as observed in study IB-200P, with approximately 120 subjects per treatment group, one-sided significance levels of 0.025, 10% drop-out rate and non-inferiority margin of -0.693 on the natural log scale (or 2-fold decrease on the original scale).

Table 4-2: Power for Non-Inferiority of BPZE1/Boostrix to Boostrix for serum IgG parameters

Serum IgG Parameter	Mean Diff Used for Sample Size Calculation (based on previous adult Ph2b study) (on natural log)	StdDev ⁺ (on natural log)	Power**			

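### Diphtheria and tetanus non-interference rests only on the Day 29 proportion at or above 0.1 IU/mL; if baseline protection is already high, a lost booster response could still pass, and a supportive concentration analysis would reveal it.

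*SAP*

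**What the plan says.** The key secondary objective (Protocol 2.2, SAP 2.2.1) is that giving BPZE1 with Boostrix does not interfere with the Day 29 IgG responses to all five Boostrix antigens. The comparison is BPZE1 + Boostrix (Group B) against Boostrix (Group C).

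SAP 8.2 uses two kinds of test:

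- **PT, FHA, PRN:** an ANCOVA of log concentration on baseline and treatment, with a limit of -0.693 (2-fold). Geometric mean titres and fold rises are also described.
- **Diphtheria and tetanus:** "For serum IgG against diphtheria and tetanus, the non-interference objective will be tested as non-inferiority of BPZE1+Boostrix group". Here the measure is the share of children at or above 0.1 IU/mL in Group B against Group C. The interval "will be calculated using the Agresti-Caffo method", and the rule is: "Non-inferiority, or non-interference, will be demonstrated if the lower limit of this 95% CI is greater than -0.1".

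Protocol 7.4.2 gives the same diphtheria and tetanus rule. The endpoint text (Protocol 2.2, SAP 3.2.2.1) refers to WHO guidelines for these two antigens, and 0.1 IU/mL is the only criterion then set. The remaining serum endpoints in SAP 3.2.2.4 concern pertussis antibodies only.

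Protocol 1.1 says that all subjects will have had an acellular pertussis primary series. Protocol 1.2 says that such vaccines usually come combined with diphtheria and tetanus.

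**The concern.** The objective asks whether BPZE1 reduces the response to Boostrix. A threshold proportion asks whether the same share of children end up above 0.1 IU/mL. The two questions agree when most children start below the threshold. They part when most start above it, because a child who was already above and does not respond still counts as a success.

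Diphtheria and tetanus are also informative antigens here. BPZE1 is a *B. pertussis* strain and supplies neither toxoid, so a difference between Groups B and C on these two antigens is not mixed with a response to BPZE1 itself. If the threshold is mostly met at baseline, a pass would reflect earlier vaccination and would say little about co-administration. As SAP 8.2 stands, a reader of the result could not tell which case applied.

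**Working it through.** **Inputs from the documents.** 108 evaluable per arm (120 less 10%); a Boostrix Day 29 proportion of at least 0.95 (SAP 4.1.2); Table 4-1 computed "with one-sided significance levels of 0.025 and non-inferiority margin of 0.1"; log-scale SDs from 0.8158 (FHA) to 1.4363 (PRN) (Table 4-2).

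**Assumptions, because the documents give no value.** Baseline proportion at or above 0.1 IU/mL (p0) from 0.85 to 0.97; Boostrix arm at Day 29 from 0.95 to 1.00; diphtheria and tetanus log SDs equal to those of the pertussis antigens; a booster rise of 4-fold or more. The unadjusted 95% interval of SAP 8.2 is used. Any stricter level under the Holm step of Protocol 7.4.2 would lower the pass rates below.

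**1. The plan's own figure.** With 0.95 in both arms, power = Φ(0.10/√(2 × 0.95 × 0.05/108) − 1.96) = Φ(3.372 − 1.96) = 92.1%, which matches Table 4-1. Exact enumeration under the planned Agresti-Caffo rule gives 89.4%.

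**2. The rule in counts.** Agresti-Caffo uses p̃ = (x + 1)/(n + 2) in each arm. The lower limit is p̃_B − p̃_C − 1.96 √[p̃_B(1 − p̃_B)/(n + 2) + p̃_C(1 − p̃_C)/(n + 2)].

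- Boostrix 108/108, BPZE1 + Boostrix 103/108: 0.9455 − 0.9909 − 1.96 × 0.0235 = −0.091. Pass.
- Boostrix 108/108, BPZE1 + Boostrix 102/108: 0.9364 − 0.9909 − 1.96 × 0.0250 = −0.103. Fail.

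So against a perfect Boostrix arm, up to five children below the threshold are tolerated.

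**3. Complete loss of the booster response.** Set the Day 29 proportion in BPZE1 + Boostrix to p0, and sum the binomial probabilities of all pairs of counts that pass:

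| Baseline p0 | Boostrix 0.95 | Boostrix 0.97 | Boostrix 0.99 | Boostrix 1.00 |
|---|---|---|---|---|
| 0.85 | 2.8% | 0.8% | 0.2% | 0.1% |
| 0.90 | 28.5% | 15.3% | 6.9% | 3.5% |
| 0.93 | 66.6% | 49.9% | 33.1% | 22.5% |
| 0.95 | 89.4% | 79.9% | 66.2% | 54.4% |
| 0.97 | – | 97.4% | 93.7% | 89.3% |

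Where p0 equals the Boostrix proportion (0.95/0.95 and 0.97/0.97), Boostrix adds nothing on this endpoint in either arm, and the pass rate is simply the power of the test.

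**4. A concentration comparison with the 2-fold limit.** This uses a two-sample t approximation with 108 per arm and ignores any gain from baseline adjustment.

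- No interference: the noncentrality is 0.693/(SD × √(2/108)). For SD 1.4363 this is 0.693/0.1955 = 3.55, power 94.2%. For SD 0.8158 it is 0.693/0.1110 = 6.24, power above 99.9%.
- Complete loss of a 4-fold rise (ln 0.25 = −1.386): pass probability about 2 × 10⁻⁸ at SD 1.4363, and smaller for smaller SDs or larger rises.
- A true loss of exactly 2-fold passes 2.5% of the time. That is only the test's level at its own margin, and should not be set against the complete-loss figures in step 3.

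**The case against.** **The criterion is a referenced choice.** The endpoint cites WHO guidelines, and comparing shares above a protective threshold is a legitimate question. This stands: it is a reason to keep the test, and the point is only that the test does not by itself address the size of the response.

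**The decisive input is missing.** Baseline seroprotection appears nowhere. Pertussis-containing vaccine within 3 years is excluded, and SAP 6.1 derives time since last vaccination in the UK as age minus 3, so up to 14 years at age 17. Baseline may therefore be lower than 0.95, and at 0.90 a complete loss would usually be detected. This stands in full and limits the claim.

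**Descriptive context may already come.** SAP section 4 plans serum summaries by group and time point in general terms, which could be read to include diphtheria and tetanus. It names neither antigen and sets no comparison.

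Four stronger readings are tempting but not supported:

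- *That loss of the whole Boostrix response could pass.* PT, FHA and PRN have a baseline-adjusted concentration test. Protocol 1.1 does report that "BPZE1 induced systemic immunoglobulin A (IgA) and immunoglobulin G (IgG) anti-pertussis antibodies (WCE, PT, FHA and PRN" rose in adults, so some masking is conceivable, but the documents give no basis for sizing it here.
- *That recent Td makes baseline high.* The exclusion covers only a "history of Td-containing vaccination (without pertussis vaccine component) within 1 month prior to Day 1", so a child vaccinated slightly earlier is eligible. Nothing suggests that such children are common.
- *That the threshold test is uninformative whenever Group A lies within 0.1 of the Boostrix arm.* With 0.90 against 1.00, complete loss passes only about 4% of the time.
- *That a concentration test should be a second condition for success.* If the two tests were independent, joint power per antigen would be about 0.894 × 0.942 = 84% at SD 1.4363, below the planned 92%. That trade-off is open to debate, and the point does not need it.

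**Conclusion.** The concern holds as a cheap improvement, for diphtheria and tetanus only. A complete loss of their booster response could be declared non-interference if baseline protection is already high: about 54% to 89% of the time at a baseline proportion of 0.95, but about 4% to 29% at 0.90, for a Boostrix arm between 1.00 and 0.95. These figures rest on an assumed baseline, 108 evaluable children per arm and the unadjusted 95% interval. Table 4-1 is not in error, and the 0.1 IU/mL criterion is not wrong. What is missing is the information needed to judge what a pass means.

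**What to change.** Keep the 0.1 IU/mL test as the formal key secondary and add to SAP 8.2, before unblinded diphtheria and tetanus results are seen:

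1. A supportive analysis of Day 29 diphtheria and tetanus IgG concentrations by the log-scale ANCOVA already used for PT, FHA and PRN (baseline and treatment). Report the Group B to Group C geometric mean ratio with its 95% CI, read against the same 2-fold limit.
2. The proportion at or above 0.1 IU/mL at baseline in all arms and at Day 29 in Group A, shown beside the B minus C difference. Group A receives no diphtheria or tetanus antigen in the trial, so its Day 29 value shows what no booster looks like.
3. A sentence saying that a pass on the proportion will be interpreted in the light of these results.

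**Cost.** Some analysis and SAP wording, with no extra subjects. Blood is drawn before vaccination and at Day 29 in every arm (Protocol Table 13-1), and SAP 4.3.3 already requires a baseline result for each test analysed. If the optional sample size recalculation is done, Protocol 7.2 has diphtheria and tetanus proportions that "will be computed in the full dataset and not by treatment group", which takes in Group A. Any baseline or Group A assays not already planned would have to be run on stored serum. The 2-fold limit and the SDs are borrowed from the pertussis antigens, and the SAP should say so.

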8.3. Secondary Endpoints Analyses

Unless otherwise specified, data will be summarized for each endpoint as described in [Section 3.2](#). Listings will be provided for all data as collected.

8.3.1. Analyses of Secondary Mucosal Secretory Immunogenicity (S-IgA) Endpoints

Descriptive statistics (GMC/GMR [also known as GMT per protocol], GMFR, seroconversion) for mucosal S-IgA against WCE, PT, FHA, PRN, and any other anti-pertussis mucosal antibodies identified during assay development will be presented at each timepoint and by treatment groups. Mucosal S-IgA will also be normalized as [specific S-IgA]/[Total S-IgA (mg/mL)].

A non-inferiority hypothesis will be tested to demonstrate BPZE1 can adequately induce pertussis specific mucosal S-IgA responses at Day 29 against WCE (GMC/GMR and GMFR) compared with Boostrix. A two-sample t-test will be used to compare the natural log-transformed GMC/GMRs between BPZE1 and Boostrix groups. The non-inferiority margin is set at 2-fold decrease or -0.693 on natural log scale. Non-inferiority will be demonstrated if the lower limit of the 95% CI of group difference on natural log scale is greater than -0.693.

To test the hypothesis that BPZE1 can adequately induce pertussis-specific mucosal S-IgA responses at Day 29, Day 85, and Day 169/EOS against WCE, PRN, PT, and FHA compared with baseline by treatment group, separate paired t-tests will be used to compare the natural log-transformed GMC/GMR at Day 29, Day 85, Day 169/EOS with the natural log-transformed GMC/GMR at baseline within each of treatment groups. The corresponding 95% CIs will be calculated on the natural log scale, then both lower and upper limits will be exponentiated to obtain the 95% CIs on the original scale.

A non-inferiority hypothesis will be tested to demonstrate that BPZE1+Boostrix induction of mucosal S-IgA immunity is non-inferior to BPZE1 at Day 29 and Day 169/EOS. Separate ANCOVA models that include baseline S-IgA and treatment group as covariates will be used to compare the natural log-transformed GMCs/GMRs between BPZE1+Boostrix and BPZE1 groups. The non-inferiority objective will be demonstrated if the lower limit of the 95% CI of group difference on the natural log scale is greater than -0.693.

Subgroup analysis by age group (6-10 years and 11-17 years, inclusive, and 10 – 17 years [for requested analyses]), time since last aP vaccination prior to study entry (<median time, \geq median time), or other baseline demographics, and by baseline antibody level (by quantile) will be conducted to examine differential responses to induction of mucosal S-IgA at Day 29 for BPZE1

and BPZE1 + Boostrix groups. In addition to descriptive summaries, a forest plot of the corresponding 95% CIs will be generated.

Mucosal S-IgA seroconversion rate is defined as 2-fold increase over baseline value or a 4-fold increase over the lower limit of assay detection (whenever the baseline value falls below the lower limit of assay detection). Mucosal S-IgA seroconversion rates will be calculated by BPZE1, BPZE1 + Boostrix, and Boostrix groups on Day 29. The 95% CI will be calculated by using Agresti-Coull method. The likelihood ratio chi-square test will be used to compare seroconversion rates among treatment groups. Additional combinations of antibody response (WCE, PT, FHA, PRN, and any additional anti-pertussis antibodies) may also be tested.

Graphics of the reverse cumulative distribution curves of each anti-pertussis mucosal antibody titer for mucosal S-IgA GMC/GMR will be generated for Day 29 by treatment group.

After natural logarithmic transformation, an ANCOVA model will be used to test the differences between treatment groups (BPZE1 vs Boostrix, BPZE1 + Boostrix vs Boostrix), with mucosal S-IgA against each of WCE, PT, PRN, FHA, and any additional anti-pertussis mucosal antibodies identified during assay development post vaccination at each of Days 29, 85, and 169/EOS as the dependent variable, vaccination as the treatment effect age, and baseline antibody value as covariates. The difference between treatment groups and the 95% CI for GMC/GMR on the natural log scale will be calculated.

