2.2 Secondary Objectives and Endpoints

Immunogenicity	
Key secondary objectives	Key secondary endpoints

 To demonstrate non-interference of immunoglobulin G (IgG) serum responses for all Boostrix-containing antigens (diphtheria, tetanus, pertussis toxin [PT], filamentous hemagglutinin [FHA], pertactin [PRN]) at Day 29 when BPZE1 is co-administered with Boostrix (BPZE1 + Boostrix vs Boostrix). 	
 BPZE1 + Boostrix induction of serum IgG against diphtheria, tetanus, and all aP antigens (PT, FHA, PRN) compared with Boostrix at Day 29 (criteria to be assessed for diphtheria and tetanus responses per WHO guidelines).
Colonization (optional substudy only)	
Secondary objective	Secondary endpoints

 To describe colonization in each of the groups: BPZE1, BPZE1 + Boostrix, BPZE1 and BPZE1 + Boostrix, Boostrix control. 	
 Proportion of subjects with colonization at either Day 92 or 99 (B. pertussis culture or polymerase chain reaction [PCR]) with prior BPZE1 immunization following re-vaccination/attenuated challenge at Day 85 (BPZE1, BPZE1 + Boostrix, BPZE1 and BPZE1 + Boostrix, Boostrix control). Expressed as absolute proportion (Yes/No).
Mucosal secretory immunogenicity (S-IgA): WCE, PT, FHA, PRN, and any additional anti-pertussis mucosal antibodies identified during assay development using geometric mean titre (GMT) and geometric mean fold rise (GMFR) unless otherwise stated.	
NOTE: To also be tested separately in subjects who participate in the optional substudy as exploratory endpoints, to assess response following re-vaccination/attenuated challenge.	
Secondary objectives	Secondary endpoints

 To demonstrate BPZE1 induction of mucosal S-IgA immunity is non-inferior to Boostrix at Day 29 as measured by antibodies to WCE (BPZE1 vs Boostrix). 	
 BPZE1 induction of mucosal S-IgA against WCE compared with Boostrix at Day 29.

 To demonstrate BPZE1 induction of mucosal S-IgA immunity is greater than baseline at Day 29 (BPZE1, BPZE1 + Boostrix). 	
 BPZE1 induction of mucosal S-IgA at Day 29 compared to baseline.

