2.2.3. Mucosal Secretory Immunogenicity (S-IgA)

- To demonstrate BPZE1 induction of mucosal S-IgA immunity is non-inferior to Boostrix at Day 29 as measured by antibodies to WCE (BPZE1 vs Boostrix).
- To demonstrate BPZE1 induction of mucosal S-IgA immunity is greater than baseline at Day 29 (BPZE1, BPZE1 + Boostrix).
- To demonstrate BPZE1 induction of mucosal S-IgA immunity remains greater than baseline over the study period and at Day 169/end of study (EOS) (BPZE1, BPZE1 + Boostrix).
- To demonstrate BPZE1 + Boostrix induction of mucosal S-IgA immunity is non-inferior to BPZE1 at Days 29 and 169/EOS (BPZE1 + Boostrix vs BPZE1).
- To assess if age, time since last aP vaccination (prior to study entry), or other baseline demographics have a differential response to induction of mucosal S-IgA immunity (BPZE1, BPZE1 + Boostrix) at Day 29.
- To assess if baseline antibody values, by baseline quantile, have variable responses at Day 29 to induction of S-IgA immunity when BPZE1 is given alone or with Boostrix (BPZE1, BPZE1 + Boostrix).
- To assess seroconversion for each of the anti-pertussis S-IgA antibodies at Day 29 (BPZE1, BPZE1 + Boostrix, Boostrix). Additional combinations of antibody response (WCE, PT, FHA, PRN, other) may also be tested.
- To assess reverse cumulative distribution curves for S-IgA at Day 29.

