$$H_0: \ln(\mu_{D29}) - \ln(\mu_{BL}) \leq 0 \text{ vs. } H_A: \ln(\mu_{D29}) - \ln(\mu_{BL}) > 0$$

After natural logarithmic transformation, a paired *t*-test will be used to test the difference of mucosal S-IgA against WCE at Day 29 compared with baseline. The superiority objective will be demonstrated if the lower limit of the 95% CI for the difference of mucosal S-IgA against WCE at Day 29 compared to baseline on the natural log scale is greater than 0. The superiority hypothesis will be tested in treatment groups BPZE1 and BPZE1 + Boostrix separately. These 2 primary comparisons will be tested at a one-sided significance level of 0.025. The study is considered a success if both primary comparisons meet statistical significance.

Sensitivity analysis for primary endpoints will be performed based on the Immunogenicity Analysis Set.

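### The BPZE1 vs Boostrix rule for Day 29 WCE S-IgA is non-inferiority with a 2-fold margin, which cannot show induction against a comparator expected to induce none

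*SAP*

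**What the plan says.** **The objective.** Protocol 2.2 lists as a secondary objective: "To demonstrate BPZE1 induction of mucosal S-IgA immunity is non-inferior to Boostrix at Day 29 as measured by antibodies to WCE". SAP 2.2.3 repeats it. No S-IgA objective in either document states superiority over Boostrix.

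**The rule.** SAP 8.3.1 introduces the test as "A non-inferiority hypothesis will be tested to demonstrate BPZE1 can adequately induce pertussis specific mucosal S-IgA responses at Day 29 against WCE". It is a two-sample t-test on log values with no baseline adjustment. On the margin: "The non-inferiority margin is set at 2-fold decrease or -0.693 on natural log scale". On the decision: "Non-inferiority will be demonstrated if the lower limit of the 95% CI of group difference on natural log scale is greater than -0.693".

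**The comparator.** Group C receives intranasal buffer plus intramuscular Boostrix. On the adult Phase 2b study, Protocol 1.1 says: "BPZE1 (but not Boostrix) was shown to induce mucosal secretory immunoglobulin A (S-IgA", with WCE among the assays named. Protocol 1.2 adds that current pertussis vaccine strategies do not provide mucosal immunity.

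**Other comparisons with Boostrix.** Later in SAP 8.3.1, "an ANCOVA model will be used to test the differences between treatment groups (BPZE1 vs Boostrix, BPZE1 + Boostrix vs Boostrix". That model covers each antigen at Days 29, 85 and 169, with baseline antibody and age as covariates and 95% CIs. The same section compares Day 29 seroconversion rates among arms with a likelihood ratio chi-square test. Both fall under the general two-sided 0.05 rule of SAP 4. Neither has a stated direction, success criterion or superiority objective.

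**The primary test.** It is a paired test against baseline within each arm: "The superiority hypothesis will be tested in treatment groups BPZE1 and BPZE1 + Boostrix separately" (SAP 8.1). Both must succeed for the study to be a success.

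**The concern.** A non-inferiority test is informative when the comparator is known to work. Here the protocol's own evidence suggests that, for mucosal S-IgA, the comparator does nothing. A lower limit above half of the control mean then excludes a large fall in S-IgA; it says nothing about a rise. Yet the SAP attaches a claim of adequate induction to it.

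The primary analysis does not fill this gap. A within-arm change from baseline cannot by itself separate a vaccine effect from a change with another cause, such as season, exposure, repeated nasal sampling or assay drift. The randomised contrast with group C can. The one such contrast that carries a decision rule has a rule that an inactive vaccine would usually satisfy.

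The same section also gives two analyses of the same Day 29 WCE contrast, an unadjusted t-test and an adjusted ANCOVA, and does not say which one the conclusion follows.

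**Working it through.** **Inputs from the documents**
- 108 evaluable subjects per arm (120 less 10%); paired effect size 0.35; two-sided 0.05 (SAP 4.1 and 4.1.1).
- Margin -0.693; pass if the lower 95% limit lies above it (SAP 8.3.1).
- Log-scale SDs for serum IgG: PT 0.8759, FHA 0.8158, PRN 1.4363 (SAP Table 4-2).

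**Assumption.** No SD is given for S-IgA. I use 0.82 to 1.44 (the range in Table 4-2, rounded), with 1.0 as an intermediate value, and extend to 2.0 and 2.5.

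**1. Reproduce the plan's figures.**
Primary paired t-test: noncentrality 0.35 × √108 = 3.64 on 107 df, giving power 95.0% per arm and 0.950 × 0.950 = 90.2% for both. The SAP states 95% and 90%.

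Serum IgG non-inferiority: noncentrality = (0.693 + assumed difference) / (SD × √(2/108)), 214 df, one-sided 0.025. This gives PT 96.95%, FHA 100% and PRN 88.25%. Table 4-2 states 97.0%, 100% and 88.2%. The method agrees with the plan's.

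**2. Apply the same formula to the S-IgA rule.** Set the true difference to 0 for a vaccine with no effect. Since √(2/108) = 0.1361, the noncentrality is 0.693 / (0.1361 × SD). The lowest observed ratio that passes is exp(1.971 × SD × 0.1361 - 0.693).

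| Log SD | Noncentrality | P(pass), true ratio 1.0 | P(pass), true ratio 0.8 | Lowest observed ratio that passes |
|---|---|---|---|---|
| 0.82 | 6.24 | >99.9% | 98.8% | 0.62 |
| 1.0 | 5.09 | 99.9% | 93.0% | 0.65 |
| 1.44 | 3.55 | 94.2% | 66.8% | 0.74 |
| 2.0 | 2.55 | 71.7% | 40.5% | 0.86 |
| 2.5 | 2.04 | 52.7% | 27.9% | 0.98 |

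The pass probability of a no-effect vaccine stays at or above 80% up to an SD of about 1.81. At every SD shown, an observed ratio below 1 can pass.

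**3. Apply a superiority rule instead** (lower limit above 0), unadjusted, 108 per arm.

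| Log SD | P(pass), no effect | Power, true 2-fold ratio | Power, true 1.5-fold ratio |
|---|---|---|---|
| 0.82 | 2.5% | >99.9% | 95.3% |
| 1.0 | 2.5% | 99.9% | 84.3% |
| 1.44 | 2.5% | 94.2% | 54.2% |
| 2.0 | 2.5% | 71.7% | 31.7% |
| 2.5 | 2.5% | 52.7% | 22.0% |

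For a between-arm effect of 0.35 SD the noncentrality is 0.35 / 0.1361 = 2.57 and power is 72.6%. These figures ignore baseline adjustment, which should raise power to the extent that baseline predicts Day 29.

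**The case against.** The other side has four good points.

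*The randomised control is used elsewhere.* A reader might infer that non-inferiority is the only between-arm S-IgA comparison with Boostrix, or the only randomised evidence of induction. The documents do not support that. SAP 8.3.1 plans the ANCOVA difference test and the seroconversion test, and a reader of their results could see whether the interval excludes no difference. SAP 8.1 also summarises GMFR in all treatment groups, so a background shift common to the arms should be visible in group C. What remains is that non-inferiority is the only BPZE1 vs Boostrix S-IgA comparison with a stated objective, direction and success criterion.

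*An inert vaccine would not carry the trial.* A reader might infer that it would. With no shift from baseline it passes each primary test only 2.5% of the time. An unrelated rise of 0.35 SD in both BPZE1 arms would give success about 90% of the time, but that is the plan's own power figure with the effect given another cause. The documents give no evidence of a drift of that size.

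*Boostrix inactivity is not established in this population.* The finding in Protocol 1.1 comes from adults, more than 90% of them estimated to have had whole-cell priming. In children primed with acellular vaccine it is an expectation. The objection stands as a caveat but does not rescue the rule: if Boostrix did induce some S-IgA, non-inferiority would still fall short of the differential response hypothesised in Protocol 1.2.

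*The size depends on an unknown SD.* This is correct. At SD 2.5 a no-effect vaccine passes about half the time, not nearly always. Even so, a rule for declaring induction should not pass an inactive product half the time.

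**Conclusion.** The concern holds for the decision rule and its wording. As written, SAP 8.3.1 would let adequate induction be declared from a result that a no-effect vaccine reaches with probability 94% to above 99.9% if the S-IgA SD lies in the serum IgG range, and 53% to 72% at SDs of 2.5 to 2.0. This rests on 108 evaluable subjects per arm, normality on the log scale, and an assumed SD. The reading of Boostrix as inactive rests on adult data.

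The needed contrast is not missing from the plan: the ANCOVA is there, without an objective or a rule. The test is also an ordinary secondary, outside the set of key secondary endpoints to which Protocol 7.4 applies the Holm procedure, and it does not enter the success criterion. The point is therefore a should-fix, not a must-fix.

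**What to change.** 1. In SAP 8.3.1 and the matching secondary objective (Protocol 2.2, SAP 2.2.3), base the Day 29 WCE S-IgA conclusion for BPZE1 vs Boostrix on the ANCOVA already planned. Conclude superiority if the lower 95% limit of the baseline-adjusted log ratio is above 0. Apply the same rule to BPZE1 + Boostrix vs Boostrix.
2. In SAP 8.1, report these two contrasts beside the within-arm GMFRs.
3. Remove the induction inference from the BPZE1 vs Boostrix non-inferiority test. If the test is kept, describe it only as excluding a more than 2-fold lower S-IgA than Boostrix.
4. Leave the non-inferiority comparison of BPZE1 + Boostrix with BPZE1 as it is; that comparator is expected to be active.

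Cost: no extra subjects, samples or models. The criterion is harder: unadjusted power is about 73% at 0.35 SD, 94% for a true 2-fold ratio at SD 1.44, and 72% for that ratio at SD 2.0. Rewording the protocol objective is an amendment and needs ethics committee approval under Protocol 11.2.1. The analysis rule itself can be set in the SAP, which governs over the protocol on planned analyses (SAP 1), with an entry in SAP 11. Either change should be made before anyone deciding on it sees Day 29 results by treatment group, including those from the interim lock.
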